As many HIV-infected children on ART survive to adulthood in sub-Saharan Africa, improving systems for disclosure and transition to adult care is a high priority. There is need for better data on transition in high volume HIV clinics in Africa, and these clinics require feasible, effective systematic approaches to improve disclosure and transition. A disclosure tool used in Namibia demonstrates effectiveness and acceptability and could be adapted for use in other settings. In addition, the Got Transition model, which was developed following broad expert consensus and programmatic evaluation in US settings, has a clear framework and useful resources relevant to pediatric HIV transition in Africa. Combining these interventions using an implementation science

approach (program evaluation, adaptation and a cluster RCT) has potential to provide high quality evidence for broader use of these approaches and to improve long-term outcomes for adolescents with HIV.

SECTION 2: OBJECTIVES

2a. Study Objective

This study aims to evaluate rates and co-factors of effective transition in HIV treatment programs in Kenya and to adapt, implement, and evaluate an Adolescent Transition Package (ATP) that combines an adapted US-based transition tool and a disclosure tool associated with improved disclosure outcomes in Namibia.

2b. Specific Objectives

Aim 1: To use programmatic data (KenyaEMR and paper files) to estimate prevalence of transition and disclosure, age at transition and disclosure, and individual-level co-factors of effective transition from pediatric to adult HIV care and retention and HIV disclosure among 10-24 year olds. To determine transition practices in Kenyan clinics using a facility survey.

Effective transition will be defined as enrollment into adult care within 6 months of exiting the pediatric care and continued clinical follow-up for at least 6 months thereafter, as evidenced by a second clinic visit recorded in the EMR.

Hypothesis: Transition will occur at varied ages (median 18 years); effective transition and earlier transition age will be associated with the presence of a transition plan and adolescent friendly services at the facility, later age at child HIV diagnosis, earlier age of HIV disclosure, parent on ART, better health status of the child at enrollment into HIV care and at transfer (CD4, WHO stage, viral load), pregnancy or marital status of the adolescent, and evidence of consistent adherence and retention prior to transition.

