Approach: *We will randomize 20 clinics to receive the ATP or no intervention (SOC) and compare disclosure and appropriate transition using pre-specified milestones among a group of children and adolescents with heterogeneous ages. During early implementation, we will monitor fidelity to the intervention using modified plan-do-study-act (PDSA) cycles. We will track implementation outcomes and factors influencing implementation during the initial ATP implementation phase (6 months). During this time, the study team will discuss and support changes to refine the tool as needed at each facility. Following the initial implementation period, HCWs will take part in focus group discussions to share their suggestions for optimizing the transition tool based on their experience. Understanding personal experiences with the tool will provide an opportunity for lessons learned and continued refinement of the intervention. At the end of the study, we will qualitatively evaluate acceptability, appropriateness and feasibility of the ATP by conducting interviews and FGDs with all HCWs from implementing sites and adolescents from a sub-set of intervention sites, purposively selecting to include participants from high and low performing facilities. We will also conduct pre-trial and post-trial surveys with adolescents and HCWs to quantitatively assess acceptability, appropriateness, feasibility of the ATP and implementation intervention fidelity. At 6-monthly intervals, we will collect readiness assessment information from adolescents in participating clinics.*

SECTION 3: STUDY OUTCOMES

Aim 1

- Prevalence of transition
- Age at transition
- Co-factors for retention
- Age at disclosure
- Co-factors of disclosure
- Individual level co-factors of effective transition
- Facility level co-factors of effective transition

Aim 2

- Adapted transition tool

Aim 3

- The primary outcome is **disclosure** among non-disclosed adolescents and **effective transition and transition readiness** among disclosed adolescents

- Disclosure will be defined as no, partial or complete disclosure. Time to disclosure and age at disclosure will also be assessed.
- Effective transition with retention in care will be defined as completing a visit on the adult day or completing a visit without a caregiver and repeat visits continuing for at least 6 months after transition.
- Transition readiness will be defined as change in response to readiness assessment questions administered every 6 months

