asked to meet with study staff. It will be emphasized that participation is completely voluntary. Adolescents and caregivers will be recruited for these focus group discussions until up to 96 adolescents have participated in 16 FGDs and 48 caregivers have participated in 8 FGDs, following the stratification pattern described in Table 2. Stratification for focus groups will include: whether or not they/ their children have completed the transition process, and the clinic model of care. Eligible participants will undergo the informed consent (caregivers and/or adolescents ≥ 18 years of age) or assent process (adolescents ages 14-17). The age of majority in Kenya is 18 years of age. Adolescents who are 18 years of age or older will provide their own adult consent, without the need for parental consent. Adolescents who are between the ages of 14 and 17 will provide written assent and their parent or primary caregiver will provide written informed consent.

Specifically, adolescents who are 18 years of age or older, or caregivers of adolescents who are between 14 and 17 years of age, who are eligible to participate, will be identified by the HIV counselors and clinicians within their respective clinics and will be told about the study during a routine clinic visit or by a phone call from a routine provider. Because adolescents typically only visit the clinic every 3 months, providers will need to call adolescents (≥ 18) or their caregivers (adolescents ages 14-17) specifically for the purpose of recruiting them into the study. HIV counselors and clinicians involved in routine clinical care at selected clinics will be given a recruitment script with talking points to help guide them on what to say. A script outlining talking points for recruitment is attached as an appendix. Adolescents aged 18 or older, or caregivers of adolescents ages 14-17, who are interested in participating or having their adolescent participate, will be asked to either stay after their visit (if already there for an appointment) or come to the clinic on a specific selected date to sign consent forms and participate in a FGD.

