A total of up to 60 providers will be selected from among all providers at intervention facilities, including 10 IDIs with ATTACH study staff. HCWs will be purposively selected to represent different cadres of HCWs who provide services for adolescents and are directly involved in implementation of the ATP. We believe that 5 providers per site (50 total), and 10 ATTACH study nurses, will give us adequate numbers to attain saturation during data collection and enough diversity in health provider cadre to ensure different perspectives are accurately represented.

A total of up to 96 adolescents will be selected for interviews. We will purposively select adolescents with a range of ages and intervention exposure. Clinic providers will assist in identifying and referring adolescents who are aware of their HIV status and have been through disclosure as well as adolescents who have been exposed to the ATP. Eligibility of adolescents will be confirmed by reviewing their chart for documentation of disclosure and transition intervention exposure. We believe that 6-10 adolescents from each site (96 total) will give us adequate numbers to attain saturation during data collection and will provide enough diversity in experiences to ensure different perspectives are accurately represented.

11b. Overview of analysis plan

Aim 1

Follow-up at 6-month post-enrollment and annually thereafter will be determined and summarized as proportion retained for given interval (e.g., 6-month retention, 12-month retention, 36-month retention) with anticipated denominator in follow-up based on enrollment date. Cofactors for loss to follow-up will be determined using Cox regression. Potential cofactors of loss to follow-up include age at enrollment, CD4, caregiver type (biologic, mother or father), age at HIV diagnosis, sex, illness or hospitalization, and evidence of transition. Proportion with evidence of transition and mean/median age of transition will be computed. Cofactors of transition will be determined including child/adolescent age, age at HIV diagnosis, evidence of disclosure, caregiver type using logistic regression. Post-transition retention will be determined and cofactors of effective transition (documented 6-month or longer follow-up after transition) will be assessed using logistic regression.

Aim 2

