Recruitment Scripts:

Study Activity	Recruitment Script
Aim 1`	
Facility Survey	Facility Survey Recruitment Script
Aim 2	
Adolescents in HIV care (48 not completed transition, 48 transitioned)	NA
	Caregiver recruitment script for adolescent IDI and FGD
	Adolescent recruitment script
Caregivers	Caregiver recruitment script
Policy makers	Policy maker/Admin/HCW recruitment script
HCW/Administrator	Policy maker/Admin/HCW recruitment script
Working group	HCW recruitment script for Workshop
Aim 3	
Pre-Trial surveys	Adolescent Recruitment Script*
Implementation Activities	HCW IS Activities Recruitment Script
Post-trial IDI	NA
	Adolescent recruitment script*
	Caregiver recruitment script*
	HCW recruitment script*
Implementation FGDs	HCW FGD Recruitment Script
Transition readiness	Adolescent recruitment script*
Disclosure readiness	Caregiver recruitment script
Post-trial surveys	Adolescent recruitment script*
	HCW recruitment script*

*Same as aim 2 document

ATTACH STUDY ANALYSIS PLAN (Finalized 2.13.2020)

SUMMARY

Study Purpose: To determine whether an adolescent transition package (with transition and disclosure tools) improves **mean transition readiness** among HIV positive adolescents in care in Kenya.

Study Design: Cluster randomized trial

Study Population and Sites:

Population:

- HIV-positive adolescents and youth between the ages of 10 and 24

Sites:

- 20 HIV clinics in Nairobi, Nakuru, Homabay and Kajiado, Kenya

Study Duration: Estimated 18 months total (enrollment and 1-year follow-up)

Randomization: 10 clinics randomized to intervention sites and 10 to control.

Intervention:

Adolescent Transition Package (ATP): The ATP will consist of a validated disclosure booklet and disclosure tracking tool, and a HCW administered transition booklet and transition tracking logs, implemented in intervention sites. HCW in intervention sites will be trained on implementation of the ATP with continued support for the clinic in the first 3 months of the intervention. In control sites, parallel data collection for primary outcomes will be conducted.

Primary endpoints: Transition readiness

Secondary endpoints: Overall clinic retention and overall viral suppression

Exploratory outcome: % with full disclosure, Time to full disclosure, Post transition retention

DATA ANALYSIS

Primary outcome: transition readiness among HIV positive adolescents age 15-24

- a. Transition readiness score overall (all domains)
- b. Treatment literacy readiness score

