- c. Self-management readiness score
- d. Communication readiness score
- e. Support readiness score

Analysis

Primary analysis ITT: Mixed effects linear regression to compare transition readiness scores (overall and by domain) over time in control and intervention sites with adjustment for multiple testing (Benjamin-Hochberg method).

Time points: Enrollment, month 6, month 12

Sample size and power table

Assumptions: 80% power, alpha 0.05, ICC 0.2, average cluster size of 50

Mean difference	SD	Number of Clusters per Arm
0.5	1	4
0.5	2	15
1.0	2	4
1.0	3	9
1.5	3	4
1.5	4	7
2.0	5	6
2.0	6	9

Secondary outcomes

- a. Overall retention in 10-24 year olds: defined as proportion of 10-24 year olds completing visits within 6 months of last visit
- b. Overall viral suppression: defined as proportion of 10-24 year olds with viral load of less than 1000 copies per ml after at least 6 months of ART

Analysis

Overall retention/suppression: Generalized estimating equations (GEE) to compare retention and viral suppression in intervention and control sites

Time-points: Baseline, month 6, month 12

Minimum detectable differences in proportions with outcomes

Assumption: 80% power, alpha 0.05, ICC 0.2, 10 clusters per arm, average cluster size of 50

Proportion with outcome in arm 1	Proportion with outcome in arm 2
0.2	0.31
0.3	0.44
0.4	0.56

0.5	0.69
0.6	0.81
0.7	0.93

Exploratory analyses

1. Post-transition retention defined as completing and adult clinic visit day after transfer to adult services and at least 1 other visit within 6 months of the adult visit (total of 2 visits):
Analysis: GEE to compare post-transition retention in intervention and control sites
2. Principal components analysis to identify the most representative components of data in the 4 domains of the readiness assessment checklist (HIV treatment literacy (Q 1-5), self-management (Q6, 7, 9-14, communication Q16-19, support 20-22) and then factor analysis to determine the most important components.
3. Proportion of children with full disclosure and time to full disclosure. Children who do not know their HIV status from HCW assessment. Child will be asked why they are taking medicine; if they report they have HIV they have reached full disclosure. If they mention any other illness or other responses they will not have reached full disclosure.
End point: Child says they have HIV in response to the question “why are you taking your medicine”
Analysis: Descriptive %, time to full disclosure

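### The SAP's post-transition retention rule treats six months as a ceiling where the protocol treats it as a minimum, so youth lost after an early second visit count as retained

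*Combined protocol and SAP*

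**What the plan says.** The SAP, Exploratory analyses, item 1, defines post-transition retention as an adult clinic visit after transfer and "at least 1 other visit within 6 months of the adult visit (total of 2 visits". The arms are compared by GEE. The item gives no minimum gap between the two visits, no denominator and no minimum observation time.

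Protocol Section 3, Aim 3, defines effective transition with retention as a visit on the adult day, or a visit without a caregiver, and "repeat visits continuing for at least 6 months after transition". Effective transition is part of the Aim 3 primary outcome there.

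For Aim 1, Section 2b asks for "continued clinical follow-up for at least 6 months thereafter", "as evidenced by a second clinic visit recorded in the EMR". Section 11b describes the same Aim 1 outcome as "documented 6-month or longer follow-up after transition".

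The SAP Summary gives the study duration as "Estimated 18 months total (enrollment and 1-year follow-up", while protocol Sections 6, 7c and 8 plan 2 years. Section 10 says that the transition tracking log is completed at transition and for the next 6 months in both arms, and that serial visit records are abstracted throughout the RCT.

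**The concern.** The two rules use the same number of months in opposite senses. Under the SAP a quick second visit is enough, and whatever follows is ignored. Under the protocol the youth must still be attending six months on. The SAP neither mentions nor justifies the change, so a reader could take its result as the protocol's effective-transition outcome although it measures something nearer to early linkage.

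There is a second, separate gap. Because the SAP sets no minimum time at risk, a youth who transfers shortly before the last data pull may be scored as not retained only because no second visit was yet due. This need not balance between arms. The protocol itself plans to examine whether the effect is larger in the first 6 months, and if the package brings transfers forward, intervention youth would have longer to record a second visit.

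**Working it through.** **Inputs**

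- Visit interval of about 3 months: protocol 7b, "Because adolescents typically only visit the clinic every 3 months".
- 24-month loss to follow-up of 25% in controls aged 16-24: Table 8.
- In the control arm over 2 years, 20% transition and 10% transition effectively: Section 11a.
- Alpha 0.05, 80% power, coefficient of variation 0.3, 100 per clinic: Section 11a and Table 8.

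**1. The plan's own figure.** The only sizing tied to this outcome is Table 8's 7 clinics per arm for transition complete, 10% against 20%. The Hayes-Moulton formula for unmatched clusters (two-sided alpha assumed) is

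c = 1 + (1.96 + 0.84)² × [p0(1−p0)/m + p1(1−p1)/m + k²(p0² + p1²)] / (p0 − p1)².

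With p0 = 0.10, p1 = 0.20, m = 100 and k = 0.3, the bracket is 0.0009 + 0.0016 + 0.09 × 0.05 = 0.0070. Then c = 1 + 7.85 × 0.0070 / 0.01 = 6.49, rounded up to 7. The figure reproduces. The SAP gives no size for post-transition retention, so no power statement changes.

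**2. The two rules applied to visit patterns** (months from the first visit)

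| Pattern | SAP item 1 | Protocol Section 3 |
|---|---|---|
| 0 only | not retained | not retained |
| 0, 1, then lost | retained | not retained |
| 0, 3, then lost | retained | not retained |
| 0, 3, 6 | retained | retained |
| 0, next visit at 7, continuing | not retained | can qualify |
| Visits without a caregiver, none in the adult clinic, continuing 6 months | not retained | qualifies |

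Each rule admits youth whom the other rejects, so they are not nested.

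**3. Size of the overcount.** Assume visits due at months 0, 3 and 6, and a constant probability d of loss after each visit. Then the SAP rule gives 1 − d, the protocol rule gives (1 − d)², and the excess is d(1 − d).

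| d | SAP | Protocol | Excess (points) |
|---|---|---|---|
| 5% | 95% | 90.3% | 4.8 |
| 10% | 90% | 81% | 9 |
| 20% | 80% | 64% | 16 |
| 30% | 70% | 49% | 21 |

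Two anchors come from the protocol:

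- *General loss.* Monthly hazard h = −ln(0.75)/24 = 0.0120. Loss by month 3 is 1 − exp(−3h) = 3.5%, and by month 6 it is 1 − exp(−6h) = 6.9%. The excess is 6.9 − 3.5 = 3.4 points.
- *Outcome-specific.* 10%/20% = 50% of control youth who transition do so effectively. Setting (1 − d)² = 0.50 gives d = 29.3%, so the SAP rule counts 70.7%. The excess is 20.7 points. As a share of eligible youth, that is 0.20 × 70.7% = 14.1% instead of 10%.

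**4. Late transfers.** If transfers were uniform over 12 months and visit recording stopped at month 12, 6/12 = half would have an incomplete 6-month window and 3/12 = a quarter would have no second visit due. Neither condition is stated in the documents, so these fractions only illustrate the mechanism.

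**The case against.** Four points on the other side have weight.

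- **Rank.** The SAP Summary lists as exploratory the percentage "with full disclosure, Time to full disclosure, Post transition retention". Nothing is sized on this outcome and the primary readiness analysis does not use it. Overall retention, a secondary outcome at baseline, month 6 and month 12, would also register some of the losses. All of this stands and limits the consequence. But overall retention is not tied to transfer, and SAP Appendix 1 lists post-transition retention under the secondary outcomes.
- **Precedent in the protocol.** The Aim 1 definition accepts a second clinic visit as evidence, which may be where the SAP rule came from. That visit is evidence of at least six months of follow-up, however, and does not replace the duration. The Aim 3 definition contains no such shortcut.
- **Size.** Table 8's 25% is general loss to follow-up, not loss after transfer, and at that rate the overcount is only 3.4 points. This stands, and is why a range is given.
- **Late transfers.** The log runs for 6 months after transition, the protocol plans 2 years, and the SAP's 18 months includes enrollment. A hard stop at month 12 is therefore not established.

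A reader might infer that any youth lost soon after transfer is counted as retained. The SAP does not do that: one adult visit alone fails, and only loss after a second visit is missed. A reader might also infer that the SAP requires two adult visits. Only the first must be an adult clinic visit; the second is any other visit, which makes the rule looser.

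**Conclusion.** The definitions conflict and nothing in the documents reconciles them. Followed literally, SAP item 1 counts as retained youth who make one early second visit and are then lost, whom Section 3 would not count. With 3-monthly visits and constant loss after each visit, the overcount among those who transition runs from about 3.4 points (general loss rate) to about 21 points (the control-arm rates in Section 11a). Visits closer together would widen it, because the SAP rule is then met sooner.

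The missing minimum observation time works in the other direction, by scoring some late transfers as failures. Its size depends on when transfers occur and when visit recording stops, so a fixed fraction of transfers cannot be declared misclassified. Nor do the documents support a claim that the trial's primary readiness result is affected. What changes is the meaning of one exploratory comparison, on an outcome that the protocol places within its primary outcome.

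**What to change.** Use one definition in Section 3 and the SAP: a first adult visit, repeat visits, and a visit in a pre-specified, bounded window around or after month 6, with no gap longer than a stated limit. The upper bound and gap limit matter, because a rule accepting any visit after month 6 would count a youth who was absent for most of a year and returned once. State whether a visit without a caregiver still counts as entry. Take visit dates from the EMR where the 6-month log ends.

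State the denominator. Transfers without a full window before the final data pull should be censored in an analysis of time to loss after transfer, or excluded from the binary analysis by the same rule in both arms. The two-visit measure can be kept under a separate name, such as early linkage.

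The change is SAP and protocol wording, using data already collected. The cost is numbers. Section 11a implies about 200 × 20% = 40 control transitions over 2 years. At a constant rate that is about 20 in 12 months, and about 10 with a full 6-month window if recording stopped at month 12 (assumption), which is very few for a GEE across 10 clinics. The comparison is also conditional on transfer, a post-randomisation event that the package may itself change, so it should remain exploratory.

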Appendix 1: Schedule for data collection

	Tools	Mo 0	Mo 3	Mo 6	Mo 9	Mo 12
Primary outcome						
Transition readiness	Transition readiness assessment	X		X		X
Secondary outcome						
% with full disclosure	Disclosure checklist	X	X	X	X	X
Time to full disclosure	Disclosure checklist	X	X	X	X	X
Age at full disclosure	Disclosure checklist	X	X	X	X	X
Post transition retention*	Transition log	X	X	X	X	X
Overall retention	EMR	X		X		X
Overall viral suppression	EMR	X		X		X

*only in adolescent models of care
